5.3.3. Covariates

The list of demographic and clinical characteristics that will be used to describe the cohort and considered for inclusion as covariates in models are provided in Table 5.3. Age, sex, state of residence and prior COVID-19 vaccinations will be obtained from the HealthVerity claims database and state vaccine registries. The HealthVerity claims database will be the sole source of all other variables.

All covariates will be assessed in the follow-up times outlined below. Categories may be collapsed or covariates may be excluded or combined if models fail to converge or if patient counts are low (Section 5.7.2). Additionally, categories with large patient counts may be split further.

Table 5.3 Demographic and Clinical Characteristics

Variable	Role(s)	Operational definition Age assessed at index date, as 2023 – year of birth. Categorized as: <5, 5-11 or 12-17 years.		
Age	-Inclusion/ exclusion			
Sex	-Inclusion/ exclusion criteria -Descriptive -Covariate	Sex assessed at index date. Male or female.		
State of residence -Inclusion/ exclusion criteria -Descriptive -Covariate -Subgroup		Defined in Section 5.2 California or Louisiana		
Payor	-Descriptive -Covariate	Payor assessed at index date. Commercial, Medicaid, Medicare Advantage, Unknown/Missing		

Variable	Role(s)	Operational definition
CDC-defined high risk for severe COVID-19(1)	-Descriptive (any high-risk condition and for each individual condition) -Covariate (each individual condition)	 Assessed using all available lookback data. Asthma Cancer, as hematologic malignancies Cerebrovascular disease Chronic kidney disease: people receiving dialysis Chronic lung diseases: bronchiectasis, COPD, interstitial lung disease, pulmonary embolism, pulmonary hypertension Chronic liver diseases: cirrhosis, non-alcoholic fatty liver disease, alcoholic liver disease, autoimmune hepatitis Cystic fibrosis Diabetes mellitus, type 1 Diabetes mellitus, type 2 Disabilities, including Down syndrome Heart conditions: heart failure, coronary artery disease, or cardiomyopathies HIV Mental health conditions: mood disorders including depression; Schizophrenia spectrum disorders Neurologic conditions limited to dementia Obesity (BMI ≥30 kg/m²) Primary immunodeficiencies Smoking, current and former Solid organ or blood stem transplantation Tuberculosis Use of corticosteroids or other immunosuppressive medications The lists of codes are provided in the Protocol Annex. Note: due to the limitations of claims data, "physical inactivity" will not be measurable and has been removed from the list.

Variable	Role(s)	Operational definition
Charlson Comorbidity Index using weights from Quan et al (2011)	-Descriptive (continuous and categorical) -Covariate (categorical)	Assessed in 6 months prior to index date. Conditions are scored as: 1 point for each of: • Chronic pulmonary disease • Rheumatologic disease • Diabetes mellitus with chronic complications • Renal disease 2 points for each of: • Congestive heart failure • Dementia • Mild liver disease • Any malignancy, including leukemia and lymphoma 4 points for each of: • Moderate or severe liver disease • HIV/AIDS 6 points for each of: • Metastatic solid tumor Categorized as: 0, 1 or 2+
Receipt of skilled nursing care and/or long-term care facility stay in year prior to index	-Descriptive -Covariate	Categorized as: 0, 1 or 2+ The list of codes is provided in the Protocol Annex Assessed in 6 months prior to index date Yes or No The list of codes is provided in the Protocol Annex
Wellness visit	-Descriptive -Covariate	Assessed in 6 months prior to index date Yes or No The list of codes is provided in the Protocol Annex
Decreased functional status	-Descriptive -Covariate	Assessed in 6 months prior to index date Yes or No The list of codes is provided in the Protocol Annex

Variable	Role(s)	Operational definition		
Influenza vaccination in 6 months prior to index	-Descriptive -Covariate	Assessed in 6 months prior to index Yes or No The list of codes is provided in the Protocol Annex		
Pneumococcal vaccination using all-available time prior to index	-Descriptive -Covariate	Assessed using all-available lookback data Yes or No The list of codes is provided in the Protocol Annex		
Herpes zoster vaccination using all-available time prior to index	-Descriptive -Covariate	Assessed using all-available lookback data Yes or No The list of codes is provided in the Protocol Annex		
Outpatient visits prior to index	-Descriptive (continuous and categorical) -Covariate (categorical)	Number of outpatient visits in 180 days prior to index Categorized as: 0, 1 or 2+ The list of codes is provided in the Protocol Annex		
Inpatient admissions prior to index	-Descriptive (continuous and categorical) -Covariate (categorical)	Number of inpatient admissions in 180 days prior to index Categorized as: 0, 1 or 2+ The list of codes is provided in the Protocol Annex		
Emergency department visits prior to index	-Descriptive (continuous and categorical) -Covariate (categorical)	Number of emergency department visits in 180 days prior to index Categorized as: 0, 1 or 2+ The list of codes is provided in the Protocol Annex		
Telehealth visits prior to index	-Descriptive (continuous and categorical) -Covariate (categorical)	Number of telehealth encounters (CPT: 99201-99215) in 180 days prior to index Categorized as: 0, 1 or 2+		
Number of documented SARS-CoV-2 tests in the 180 days prior to index	-Descriptive (continuous and categorical) -Covariate (categorical)	Number of visits in any setting with CPT in 180 days prior to index: 86408, 86409, 0225U, 0226U Categorized as: 0, 1 or 2+		
Prior post- COVID-19 conditions	-Descriptive -Covariate	Assessed using all-available lookback data, any encounter regardless of setting with ICD- 10-CM U09.9 "Post-COVID-19 condition" Yes or No		

Variable	Role(s)	Operational definition
Prior COVID-19 diagnosis	-Descriptive -Covariate	Any encounter with ICD-10-CM code: U07.1 between 90 and 365 days prior to index Yes or No
Prior bivalent BA.4/5 COVID-19 vaccine	-Descriptive -Subgroup	Where the BNT162b2 XBB.1.5 vaccine is the exposure of interest. Using all-available lookback data, received bivalent BA.4/5 COVID-19 vaccine (regardless of brand) prior to index Yes or No The list of codes is provided in the Protocol Annex
At least two prior doses of mRNA vaccine and no bivalent BA.4/5 COVID-19 vaccine	-Descriptive -Subgroup	Where the BNT162b2 XBB.1.5 vaccine is the exposure of interest. Using all-available lookback data, received at least two prior doses of mRNA vaccine (regardless of formulation) and did not receive bivalent BA.4/5 COVID-19 vaccine. Yes or No
		Note: the doses must be at least 21 days apart. The list of codes is provided in the Protocol Annex
Never COVID-19 vaccinated	-Descriptive -Subgroup	Using all-available lookback data, no prior receipt of a COVID-19 vaccine (regardless of formulation)
		Note: Patients without prior bivalent BA.4/5 COVID-19 vaccine and either a single mRNA vaccine dose or two mRNA doses less than 21 days apart are categorized as "No", as per Section 5.2.3.
		Yes or No The list of codes is provided in the Protocol Annex
Time since last COVID-19 vaccine	-Descriptive -Subgroup	Using all-available lookback data, time in months between index date and prior receipt of a COVID-19 vaccine (regardless of formulation) The list of codes is provided in the Protocol Annex

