Influenza emergency department visit	HV Claims	Emergency department visit with ICD-10-CM code: J09-J11
Influenza outpatient encounter	HV Claims	Outpatient encounter with ICD-10-CM code: J09-J11
Negative control outcome, such as accidental injury, ingrown toenail or atopic dermatitis	HV Claims	Any encounter regardless of setting, with ICD- 10-CM code for negative control outcomes (codes in annex)

TABLE 5. COVARIATES

Variable	Data source(s)	Operational definition
		Age assessed at index date. Where not stratified, age will be adjusted as:
	HV	For aims 1 and 4, age will be directly adjusted using indicator variables for 18-49, 50-64 and 65+.
Age	Claims/CAR	For aim 2, age will be directly adjusted using indicator variables for <5 years, 5-11 and 12-17 years.
		For aim 5, age will be included in the propensity score as a continuous variable.
Sex	HV Claims/CAR	Sex assessed at index date as male, female or unknown. Models will be adjusted for sex when not stratified by sex.
State of residence	HV Claims	Models will be adjusted for state (California or Louisiana), except those which are stratified by state.

disease, or cardiomyopathies HV Claims He Mental health conditions: mood disorders including depression; Schizophrenia spectrum disorders Neurologic conditions limited to dementia Obesity (BMI ≥30 kg/m² or ≥95 th percentile in children) Physical inactivity Primary immunodeficiencies Smoking, current and former Solid organ or blood stem transplantation Tuberculosis Use of corticosteroids or other immunosuppressive medications Note: racial/ethnic minority status is included in the high risk definition, but not included in HealthVerity data and therefore unable to be	HV Claims	 Cystic fibrosis Diabetes mellitus, type 1 Diabetes mellitus, type 2 Disabilities, including Down syndrome Heart conditions: heart failure, coronary artery disease, or cardiomyopathies HIV Mental health conditions: mood disorders including depression; Schizophrenia spectrum disorders Neurologic conditions limited to dementia Obesity (BMI ≥30 kg/m² or ≥95th percentile in children) Physical inactivity Primary immunodeficiencies Smoking, current and former Solid organ or blood stem transplantation Tuberculosis Use of corticosteroids or other immunosuppressive medications Note: racial/ethnic minority status is included in the high risk definition, but not included in HealthVerity data and therefore unable to be

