5.2.1. Inclusion Criteria

- Born in 2006-2023 (as age 0-17 years in 2023, owing to the data providing year but not month or day of birth).
- At least six months of pharmacy and medical enrollment in HealthVerity prior to index date (FDA EUA date per age group vaccine). Six months was selected to allow for analysis to include children age <1yr. A gap of up to 30 days will be allowed.
- Have been a State of California/Louisiana resident for at least six months prior to index date (FDA EUA date per age group and vaccine). A gap of up to 30 days will be allowed.

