Baseline Chronic Medical Conditions (Yes/No)	Clinical characteristic	HealthVerity	Proportions of patients with at least one medical coding for each of the chronic medical conditions listed below during the baseline period (not mutually exclusive) will be identified. Reported as counts and percentages. • Having any of the conditions below

Variable	Role	Data source	Operational definition
Variable	Role	Data source	 ○ Asthma ○ Cancer ○ Cerebrovascular disease ○ Chronic kidney disease ○ Chronic lung diseases limited to: ■ Bronchiectasis ■ COPD (Chronic obstructive pulmonary disease) ■ Interstitial lung disease ■ Pulmonary embolism ■ Pulmonary hypertension ○ Chronic liver diseases limited to: ■ Cirrhosis ■ Non-alcoholic fatty liver disease ■ Alcoholic liver disease ■ Autoimmune hepatitis ○ Cystic fibrosis ○ Diabetes mellitus, type 1 ○ Diabetes mellitus, type 2 ○ Disabilities, including Down syndrome ○ Heart conditions (such as heart failure, coronary artery disease, or cardiomyopathies) ○ Mental health conditions limited to: ■ Mood disorders, including depression ■ Schizophrenia spectrum disorders ○ Neurologic conditions limited to dementia ○ Obesity (BMI >30 kg/m2 or >95th percentile in children) ○ Solid organ or blood stem cell transplantation ○ Tuberculosis Note: racial/ethnic minority status is included in the high risk definition, but not included in Health/verity data and therefore unable to be assessed. Pregnancy is included in the high risk definition, but is an exclusion criteria for each aim in this protocol
			and therefore is not listed here. Given the nature of administrative claims data, obesity islikely to be undercaptured.
Quan-Charlson Comorbidity Index (CCI) Score	Clinical characteristic	HealthVerity	CCI will be defined during the baseline period and will be used to assign patients to CCI groups: 0, 1, 2, 3+. Reported as min, max, median (Q1-Q3) and mean (SD), as well as counts and percentages for CCI groups.
COVID-19 Vaccination Status	Clinical characteristic	HealthVerity	COVID-19 vaccination status (described later) during the baseline period. Categories will be reported as counts and percentages.
Number of All-cause	Patient	HealthVerity	Number of hospitalizations for any cause during the

Variable	Role	Data source	Operational definition

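### The Aim 2 (pediatric) SAP lists obesity as BMI ≥30 kg/m² only and drops, without explanation, the protocol's 95th-percentile criterion for children

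*SAP*

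**What the plan says.** - **Protocol, Table 5 (Section 8.3).** The high-risk list defines obesity as "Obesity (BMI ≥30 kg/m² or ≥95 th percentile in children". Section 8.7.2 states that the Aim 2 models will be adjusted for the Table 5 covariates.
- **Aim 2 SAP, Section 5.2.1.** The cohort is pediatric only: "Born in 2006-2023 (as age 0-17 years in 2023, owing to the data providing year but not month or day of birth".
- **Aim 2 SAP, Table 5.3 (Section 5.3.3).** The corresponding entry is "Obesity (BMI ≥30 kg/m²", with no percentile criterion. The role of the high-risk group is given as "Covariate (each individual condition", so obesity enters the model on its own. It also feeds the descriptive summary of children with any high-risk condition. On how the conditions are identified, the table says: "The lists of codes are provided in the Protocol Annex".
- **Aim 1 (adult) SAP, Table 5.3.** The obesity line is the same as in the Aim 2 SAP.
- **Aim 3B SAP, Table 1 (Section 5.3).** This aim includes both adults and children, and it keeps a percentile rule: "Obesity (BMI >30 kg/m2 or >95th percentile in children".

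**The concern.** The part of the protocol definition written for children is missing from the one VE analysis that contains only children. What remains is the general BMI cut-off, worded as in the adult SAP.

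Two things are at stake. First, obesity is meant to be an adjustment variable. If part of the obese group is coded as non-obese, any confounding by obesity in that part stays in the adjusted hazard ratio. Results are also reported for ages 6 months-4 years, 5-11 and 12-17, so the same fixed cut-off applies in every stratum. Second, the descriptive count of children with any high-risk condition would be too low.

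Sampling error may not hide a small bias. For a VE of 30% in 3 million children, Aim 2 SAP Table 5.4 shows a 95% CI of 29 to 31 at 10,000 cases per 100,000, and 26 to 34 at 1,000 per 100,000.

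**Working it through.** No figure in the plan rests on this definition, so there is nothing to reproduce. The check is a comparison of texts, followed by an illustration of scale.

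**Step 1: the definitions side by side**

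| Document | Population | Obesity rule |
|---|---|---|
| Protocol Table 5 | all aims | BMI ≥30, or ≥95th percentile in children |
| Aim 1 SAP Table 5.3 | adults | BMI ≥30 |
| Aim 2 SAP Table 5.3 | ages 0-17 | BMI ≥30 |
| Aim 3B SAP Table 1 | adults and children | BMI >30, or >95th percentile in children |

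**Step 2: logical relation.** Let A be BMI ≥30 and B be ≥95th percentile. The protocol rule is A or B; the Aim 2 SAP rule is A alone. A is contained in A-or-B. Measured against the protocol, the SAP wording can therefore only lose children (those in B but not in A) and can add none. This is a statement about the two written rules, not about the coded data.

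**Step 3: is the change explained?** The note under the Aim 2 high-risk list explains why physical inactivity was removed. It says nothing about obesity. Other Aim 2 entries were adapted for children, for example the age bands and several 6-month lookbacks. The obesity line therefore reads like adult text carried over, although that is an inference.

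**Step 4: scale (illustration only).** The prevalences, the obesity-outcome ratio and the capture rates below are assumed, because the documents give none. The true VE of 30% lies in the 20-40% range of Aim 2 SAP Section 5.5.

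Let p0 and p1 be obesity prevalence in unvaccinated and vaccinated children, R the obesity-outcome ratio, and s the fraction of obese children captured, with no false positives.

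- Obese share left among those coded non-obese: q = p(1−s)/(1−ps)
- Bias factor: b = [1+q1(R−1)]/[1+q0(R−1)]
- Apparent VE: 1 − 0.70 × b

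Example with p0 = 0.20, p1 = 0.10, R = 2.0:

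- s = 0: b = 1.10/1.20 = 0.9167; VE = 1 − 0.70 × 0.9167 = 35.8%.
- s = 0.5: q0 = 0.10/0.90 = 0.1111 and q1 = 0.05/0.95 = 0.0526; b = 1.0526/1.1111 = 0.9474; VE = 33.7%.
- s = 1: b = 1; VE = 30.0%.

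Results over R = 1.2, 1.5 and 2.0, for three prevalence pairs (p0/p1):

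| p0 / p1 | s = 0 | s = 0.25 | s = 0.5 | s = 1 |
|---|---|---|---|---|
| 0.20 / 0.15 | 30.7-32.9% | 30.6-32.5% | 30.4-31.9% | 30.0% |
| 0.20 / 0.10 | 31.3-35.8% | 31.1-34.9% | 30.8-33.7% | 30.0% |
| 0.25 / 0.15 | 31.3-35.6% | 31.1-34.8% | 30.8-33.8% | 30.0% |

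A wider contrast, 0.25 against 0.10 with R = 2.0 and s = 0, gives 1 − 0.70 × (1.10/1.25) = 38.4%.

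These figures compare partial with full capture. The wording accounts only for the difference between capture under the two rules. If it lowered s from 0.5 to 0.25, for instance, the largest change in the table is 34.9 − 33.7 = 1.2 points. The sign reverses if obesity is more common among vaccinated children.

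**The case against.** The strongest reply is that the wording in Table 5.3 is a label, not the algorithm. The covariate comes from claims alone, and the data elements described in Aim 2 SAP Section 5.4.2 include diagnoses and procedures but no measured BMI. A child is recorded as obese through codes in the Annex, which is not available here. If that list still holds the pediatric percentile codes or general obesity diagnoses, the shortened label changes nothing in the data. This stands, and it makes the effect on the data conditional. The SAP would still misdescribe its own covariate.

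Other points also have weight:

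- The Aim 3B SAP says obesity is likely under-captured in claims even with a percentile rule, so some of these children would be missed under either wording.
- Obesity is one of 20 listed conditions. It may be dropped when events per variable are low and its standardized mean difference is below 0.1 (Section 5.7.5). Negative control outcomes are planned as a check on residual confounding (Section 5.7.6).
- Protocol Section 8.7 lets the SAP modify the protocol. That permits a change, but it does not show that this one was intended.
- Aim 3B is only a partial precedent. It uses > where the protocol uses ≥, and obesity there is a baseline characteristic, absent from both the matching criteria and the regression covariates.

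A reader might infer that most obese children are adjusted as non-obese, or that the covariate does almost nothing in the youngest group. The documents support neither, because they give no pediatric BMI distribution, percentile values or obesity prevalence. Nor can one say that no child is wrongly coded obese, or that every child in the gap is missed; both depend on coding accuracy and on the unseen list.

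**Conclusion.** The inconsistency is established from the text. The children-only SAP omits the child criterion that the protocol makes part of the Aim 2 adjustment set, and it gives no reason. Followed as written, the SAP rule is narrower than the protocol rule and can only lose obese children relative to it.

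Whether any child is actually recoded depends on the Annex code list. If the list follows the SAP wording, adjustment for obesity is weakened and the count with any high-risk condition is understated. The share of children affected and the VE shift cannot be computed from the documents. The shift is likely small, and its direction is unknown; the illustrative figures depend on assumed prevalences, risk ratios and capture rates and are not estimates. This is a minor correction worth making, and it does not undermine the Aim 2 analysis.

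**What to change.** In Aim 2 SAP Table 5.3, restore the protocol entry "Obesity (BMI ≥30 kg/m² or ≥95 th percentile in children", keeping the protocol's ≥ in both places and not the > of the Aim 3B SAP. If the omission was deliberate, add a sentence of justification beside the existing note on physical inactivity. In either case, confirm that the Annex code list for obesity includes the pediatric percentile codes. The difference in inequality signs in the Aim 3B SAP can be reconciled at the same time.

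If the code list already includes those codes, the cost is one line of text. If the list was narrowed, the obesity covariate and the any-high-risk summary must be rebuilt and the Aim 2 adjusted models rerun. No new data are needed.

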the high risk definition, but not included in HealthVerity data and therefore unable to be assessed. Pregnancy is included in the high risk definition, but is an exclusion criteria for each aim in this protocol and therefore is not listed here. Given the nature of administrative claims data,		the high risk definition, but not included in HealthVerity data and therefore unable to be assessed. Pregnancy is included in the high risk definition, but is an exclusion criteria for each aim in this protocol and therefore is not listed here. Given the nature of administrative claims data, obesity, physical inactivity, and smoking are likely

Variable	Data source(s)	Operational definition
Charlson-Deyo Comorbidity Index, ²⁵ operationalized as scores of 0, 1 or 2 using	HV Claims	Assessed using all-available lookback data. Codes are in annex, and conditions are scored as: 1 point for each of: Myocardial infarction CHF Peripheral vascular disease Cerebrovascular disease Dementia Chronic pulmonary disease Connective tissue disease Peptic ulcer disease Mild liver disease Diabetes mellitus without chronic complications 2 points for each of: Hemiplegia Moderate to severe renal disease Diabetes with chronic complications Cancer, including leukemia and lymphoma 3 points for moderate or severe liver disease 6 points for each of: Metastatic carcinoma HIV/AIDS
Receipt of skilled nursing care and/or long-term care facility stay in year prior to index	HV Claims	Codes in Annex
Wellness visit	HV Claims	Codes in Annex
Decreased functional status	HV Claims	Codes in Annex
Influenza vaccination in year prior to index	HV Claims	Vaccines will be enumerated as per section 8.2. Influenza vaccines are recommended annually, and therefore we will measure influenza vaccination in prior year.

Variable	Data source(s)	Operational definition
Pneumococcal vaccination using all-available time prior to index	HV Claims	Vaccines will be enumerated as per section 8.2. Pneumococcal vaccinations are generally not repeated events, and therefore we will use allavailable lookback data to assess receipt.
Herpes zoster vaccination using all-available time prior to index	HV Claims	Vaccines will be enumerated as per section 8.2. Herpes zoster vaccinations are generally not repeated after primary series, and therefore we will use all-available lookback data to assess receipt.
Outpatient visits prior to index	HV Claims	Number of outpatient visit(s) in 180 days prior to index

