8.5. Study Size

Since the current study utilizes retrospective deidentified data without ability to recruit to a target, sample size calculations are not applicable. Further, this is a descriptive study without *a priori* specified hypotheses.

Initial data feasibility work has revealed approximately 19 million persons in the state of California with claims available in HealthVerity, among which approximately 25% are pediatric and 75% adult. Among these, approximately 12 million have at least one year of continuous medical and pharmacy enrollment. By end of 2023, we expect to have finished contracting to add approximately 565,000 additional persons. The proportion of these additional persons who will have 1-year continuous enrollment, and therefore the sample size estimates below have taken the conservative approach to not yet include these people.

We have identified 63% of persons in the claims data have at least one COVID-19 vaccine, and 16% received at least one bivalent dose. The claims population we have is not a random sample of Californians and may differ from the state's population in systematic ways (e.g. the age distribution). While differences may exist, we have high confidence in our ability to represent vaccination status for the individuals in our claims population.

We expect to begin to see XBB doses in data delivered in November 2023. Assuming uptake similar to that seen with the BA.4/5 vaccine, and non-differential uptake by age groups, we could anticipate in California:

(25% of 12 million are pediatric)*(16% uptake)*(60% of doses were Pfizer-BioNTech)

~ 288,000 pediatric XBB doses in California

(75% of 12 million are adult)*(16% uptake)*(60% of doses were Pfizer-BioNTech)

~ 864,000 adult XBB doses in California

Additional doses will be observed in Louisiana. In order to maintain patient de-identification, outcomes, covariates and subgroups will have at least 10 people in each category for inclusion in outputs. Throughout the protocol, this is referred to as "If sample size allows".

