		Annex
Receipt of skilled	-Descriptive	Assessed in the year prior to index date
nursing care	-Covariate	Yes or No
and/or long-term		The list of codes is provided in the Protocol
care facility stay in		Annex
year prior to index		
Wellness visit	-Descriptive	Assessed in the year prior to index date
	-Covariate	Yes or No
		The list of codes is provided in the Protocol
D 1	D :::	Annex
Decreased	-Descriptive	Assessed in the year prior to index date
functional status	-Covariate	Yes or No The list of codes is appriited in the Protocol
		The list of codes is provided in the Protocol

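### Aim 2 SAP: six-month windows for the wellness visit, long-term care, functional status, Charlson and influenza vaccination shorten the protocol's lookback without explanation and may under-adjust for preventive-care behaviour

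*SAP*

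**What the plan says.** The Aim 2 SAP (section 5.3.3, Table 5.3) scores Charlson conditions as "Assessed in 6 months prior to index date. Conditions are scored as: 1 point for each of", followed by its weights. Wellness visit, decreased functional status and skilled nursing or long-term care are also assessed over six months. The long-term-care row is nevertheless labelled "Receipt of skilled nursing care and/or long-term care facility stay in year prior to index". Influenza vaccination is assessed over six months as well.

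Protocol section 8.3, Table 5, says of Charlson "Assessed using all-available lookback data. Codes are in annex, and conditions are scored as", sets one year for long-term care, and sets one year for influenza vaccination on the ground that it is given annually. It states no window in the rows for wellness visit or functional status. For those two, only the general rule in section 8 applies: all data from 1 December 2018.

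The Aim 1 SAP, Table 5.3, says "Assessed in the year prior to index date" for long-term care, wellness visit and functional status.

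The Charlson versions also differ. The protocol uses Charlson-Deyo, with "2 points for each of: Hemiplegia Moderate to severe renal disease" among its entries. The Aim 2 SAP names a 2011 set of weights, and hemiplegia appears at no weight level.

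**The concern.** Six months is the Aim 2 enrollment minimum, chosen so that infants can enter. Table 5.3 applies it to older children too, where a longer history is often available. A wellness visit is typically a yearly event and a marker of preventive-care behaviour, which plausibly relates both to being vaccinated and to having a coded COVID-19 encounter. A window that misses part of the yearly visits puts attenders into the No group, and the adjusted pediatric VE keeps some of that confounding. Influenza vaccination has the same problem: a window from mid-March to mid-September leaves out the preceding autumn and most of the winter.

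The enrollment minimum does not force this choice. The same table uses all available lookback for each high-risk condition and looks back 365 days for a prior COVID-19 diagnosis. The planning figure of 3 million children is 25% of a Californian population of which "approximately 12 million have at least one year of continuous medical and pharmacy enrollment".

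**Working it through.** **Calendar.** The index date is 11 September 2023 (Aim 2 SAP, 5.7.3) and a month is 30 days (5.7.1).
- Six months = 180 days, so the window opens on 15 March 2023.
- A 365-day window opens on 11 September 2022.
- All available lookback from 1 December 2018 spans 1,745 days, and 1,745/180 = 9.7 times the six-month window.
- If yearly visits were spread evenly (assumption), six months would catch 180/365 = 49% of them.

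**The plan's own figures.** 0.25 × 12,000,000 × 0.16 × 0.60 = 288,000 doses, as stated in section 5.5. Uptake of BNT162b2 is therefore 0.16 × 0.60 = 9.6%. In Table 5.4, with 3,000,000 children and VE 30%, the 95% CI is 29 to 31 at 10,000 cases per 100,000 (half-width 1 point) and 26 to 34 at 1,000 (half-width 4 points).

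**Illustrative residual bias from the wellness visit.** Only the 9.6% uptake and the 30% VE (inside the 20 to 40% planning range) come from the documents. The rest is assumed:
- share of children with a yearly visit, p = 0.5 or 0.7
- share of those visits inside the six-month window, c = 0.50 or 0.65
- attenders' vaccination probability relative to non-attenders, k = 2 or 3
- attenders' rate of coded encounters relative to non-attenders, R = 1.2 or 1.5

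Non-attenders are vaccinated with probability v0 = 0.096/(1 − p + kp), attenders with k·v0. A Mantel-Haenszel rate ratio is taken over the two strata of the six-month flag.

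Worst corner (p = 0.5, k = 3, R = 1.5, c = 0.5): v0 = 0.048 and k·v0 = 0.144. The non-attender unvaccinated rate is set to 1.

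| Six-month flag | Vaccinated share | Unvaccinated share | Events, vaccinated | Events, unvaccinated |
|---|---|---|---|---|
| Yes | 0.25 × 0.144 = 0.036 | 0.25 × 0.856 = 0.214 | 0.036 × 1.5 × 0.7 = 0.0378 | 0.214 × 1.5 = 0.321 |
| No | 0.036 + 0.5 × 0.048 = 0.060 | 0.214 + 0.5 × 0.952 = 0.690 | (0.036 × 1.5 + 0.024) × 0.7 = 0.0546 | 0.321 + 0.476 = 0.797 |

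Numerator: 0.0378 × 0.214/0.25 + 0.0546 × 0.690/0.75 = 0.08259. Denominator: 0.321 × 0.036/0.25 + 0.797 × 0.060/0.75 = 0.10998. The ratio is 0.751, so VE reads 24.9%.

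Mildest corner (p = 0.7, k = 2, R = 1.2, c = 0.65): VE reads 28.9%. Over all 16 combinations the range is 24.9 to 28.9%, that is 1.1 to 5.1 points below 30%.

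A second calculation, standardised to the vaccinated, assumes a yearly visit in 70 to 80% of vaccinated and 50% of unvaccinated children, half of them captured. It gives 28.3 to 24.6% for R of 1.2 to 1.5, and down to 21.3% if R is 2.0.

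**Comorbidity.** The same standardised calculation for a rare condition (assumed 5% of vaccinated and 3% of unvaccinated, half captured, R 1.2 to 2.0) gives 29.9 to 29.3%, a shift of 0.1 to 0.7 points.

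**Charlson lists side by side.** Of the protocol's 17 conditions, six are absent from the Aim 2 list: myocardial infarction, peripheral vascular disease, cerebrovascular disease, peptic ulcer disease, diabetes without complications, and hemiplegia. Five more change category (0, 1, 2+) through new weights: heart failure, dementia and mild liver disease go from 1 to 2; renal disease and diabetes with complications go from 2 to 1. So 6 + 5 = 11 of 17 conditions, taken singly, change category. Hemiplegia alone moves from 2+ to 0.

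**The case against.** The strongest reply is that the windows are deliberate and permitted. Protocol section 8.7 lets the SAP modify its plans, and the Aim 2 SAP (5.1) says lookback varies by covariate. Each SAP largely ties its windows to its enrollment minimum, and Aim 1 likewise shortens Charlson, to one year. A window that every included child must have observed avoids ascertainment that depends on length of history. This stands as far as it goes. A reader might infer a breach of the protocol, but the documents show an unexplained departure, and for wellness visit and functional status it is a departure only from the general lookback rule.

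A reader might also infer that hemiplegia was deleted by mistake and should be given 2 points. The documents do not support that. It is one of six conditions lost in a change of index version, and whether the named version contains it cannot be checked here.

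Nor do the documents show that comorbidity confounding is under-adjusted. Each high-risk condition enters the model separately on all available lookback, including cerebrovascular disease, both diabetes types, heart conditions and disabilities. Whether the disability codes cover hemiplegia depends on the Annex.

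Other safeguards count. Pneumococcal vaccination stays on full lookback, and negative control outcomes (5.7.6) can prompt a changed confounder set and bias-corrected VE. These reduce the concern without removing it. The outpatient, inpatient, emergency and telehealth counts all use 180 days, so they cannot see an older visit and help only through correlation. The negative controls act after the fact.

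**Conclusion.** The point holds as an avoidable loss of confounder information. The departures from explicit protocol windows are Charlson, long-term care and influenza vaccination, and the long-term-care row contradicts its own label. The main statistical consequence is misclassification of yearly preventive-care markers. Under the assumed inputs, a true VE of 30% would read roughly 1 to 5 points too low, which equals or exceeds the 1-point half-width that Table 5.4 gives for a common outcome.

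That is an illustration. The model has one confounder, ignores every other covariate, and defines the yearly visit as the confounder, so its finding that a 12-month flag removes the bias is built in. The direction also follows from assuming that attenders are more likely both to be vaccinated and to have a coded encounter; with a lower encounter rate among attenders the bias would reverse. A reader might take the 1 to 5 points as a demonstrated bias in the pediatric VE, but the documents give none of the prevalences or rate ratios needed for that. Any comorbidity effect is likely small.

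**What to change.** In Aim 2 SAP Table 5.3:
- Assess wellness visit, skilled nursing or long-term care, functional status and influenza vaccination over 365 days before index, or over available history if shorter, with an indicator for less than 12 months of history. For wellness visit and functional status this is still shorter than the protocol's general rule, so state the reason (a yearly marker, consistent with Aim 1).
- Assess Charlson over all available lookback, as in the protocol.
- Make the long-term-care label and its rule agree.
- Check the Charlson condition list, including the absence of hemiplegia, against the index version it names, or return to the protocol's index. Record the reason for any change of version.
- Keep the six-month windows as a sensitivity analysis.

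The cost is SAP wording and a code parameter, with no new data. The downside is that length of history will vary between children. The short-history indicator and the six-month sensitivity analysis show whether that matters.
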